In order to improve the implementation of prehabilitation, we have, on the one hand, streamlined the content of prehabilitation, improved the implementation process, and published a prehabilitation guideline in our previous prehabilitation research; on the other hand, we hope to explore a more feasible management model. Multidisciplinary collaboration is the foundation of prehabilitation.

“Internet+medical service” has become a new mode of modern medical management, which can intuitively and vividly deliver information to patients and obtain effective feedback, enhance the efficiency of doctor-patient communication, and improve the enthusiasm of patients to participate in the perioperative management, which is especially suitable for the popularization and application of patient-oriented prehabilitation, and reduces the waste of medical human resources and economic burden. Under the normalization of epidemic prevention and control, the Internet and online diagnosis and treatment will provide a more effective way for preoperative prehabilitation.

“Internet +” perioperative management is in line with the trend of China's medical service innovation and development. The application of the Internet in the field of healthcare is becoming more and more widespread, and has also been strongly supported and advocated by the state. 2016, the CPC Central Committee

and State Council issued the “Healthy China 2030” planning program, in 2017, the General Office of the State Council issued the “China's medium- and long-term plan for the prevention and treatment of chronic diseases (2017-2025),” and The Opinions on Promoting the Development of “Internet+Medical Health” issued by the General Office of the State Council in 2018, all emphasize the construction of a health information service system, innovation, exploration and improvement of the “Internet+” medical and health service system, the development of telemedicine, health consultation and health management services, and the enhancement of clinical and health care services. consulting, health management services, and strengthen the integration, sharing and application of clinical and scientific research data [10-11].

2021;47(5):929-930.

2. Purpose of the study

- 1) Exploration and development of a smartphone-based online prehabilitation management application for VATS surgery for lung cancer;
- 2) Conduct perioperative stereoscopic assessment of functional status and quality of life in VATS surgery for lung cancer;
- 3) Construction of an Internet-based short-term home-based multicomponent prehabilitation model for VATS surgery for lung cancer in combination with wearable exercise devices;
- 4) Evaluation of the clinical feasibility and clinical significance of Internet + wearable device prehabilitation applied to VATS surgery for lung cancer.

3. Content of the study

3.1 Construction of a user-screen friendly version of the Multi-Link Pre-Rehabilitation online application experience:

- 1) Introduction to Prehabilitation: A short video is used as the main format, supplemented by pictures and brief text, to introduce the basic contents

and significance of Prehabilitation;

- 2) Details of the prehabilitation program: details of the purpose of the prehabilitation, the timing of the essential elements and the details of the contents in concise and easy-to-understand language text and pictures;
- 3) Scheduling: Provide examples of prehabilitation weekly scheduling. In the pre-operative assessment clinic, the doctor conducts a pre-operative assessment of the patient, combining the patient's personal habits and arrangements, and the doctor and patient work together to develop an individualized prehabilitation plan;
- 4) Demonstration of follow-up exercises: including breathing training follow-up videos, anaerobic exercise follow-up videos, aerobic exercise warm-up follow-up videos, etc., which are suitable for elderly patients with debility, patients with mildly reduced activity tolerance and patients with significantly reduced activity tolerance. It also includes synchronized instruction, so that patients can complete efficient follow-up exercises without leaving home;
- 5) Three-dimensional assessment of perioperative functional status and quality of life: the application realizes online functional status assessment, including NRS2002 Nutritional Risk Screening, Hospitalization Anxiety and Depression Scale (HADS), Quality of Recovery Rating Scale (QoR-15), and WHO Disability Assessment Scale version 2.0 (WHODAS 2.0), etc., with the patients completing the questionnaires online; and also includes the self-

measurement of the 6-min walking distance (6MWD). At the same time, it includes the self-measurement of 6min walking distance (6MWD), and patients can complete the self-measurement of 6MWD according to the prompts of the application;

- 6) Implementation and feedback function: It can realize the guidance and adjustment of prehabilitation strategy after reassessment; and set up functions such as daily reminder and prehabilitation activity record.

3.2 To conduct a study on the impact of short-term internet + wearable device-based home-based multilink prehabilitation management on preoperative functional status and prognosis of patients undergoing VATS surgery compared to the traditional model.

A prospective randomized controlled single-blind clinical trial. 64 patients with diagnosed lung occupations intended for VATS surgery were to be included. They were randomized into the “Internet+” group and the traditional prehabilitation control group.

- 1) Sixty-four adults aged ≤ 75 years; suspected lung cancer intended for VATS lobectomy/sublobar resection were selected for the study.
- 2) Prehabilitation intervention: Both groups underwent individualized home-based multimodal prehabilitation strategies, and the timing of the prehabilitation intervention was about 2 weeks from the time the doctor and the patient jointly decided to have the surgery to 1 day before the surgery. The content of prehabilitation included smoking cessation, aerobic training,

anaerobic exercise, nutritional optimization and psychological support. The "Internet+" group used the management mode of online application + wearable devices; the traditional prehabilitation group used the traditional management mode of preoperative preaching + paper records + regular weekly reminders from medical staff.

- 3) Study endpoints: The follow-up period was from the time when the surgeon and the patient decided to operate to 30 days after the operation. The 6MWD was used as the primary assessment of perioperative functional status and the primary endpoint of the study, and patients were evaluated at enrollment, before surgery, and 30 days after surgery. Secondary endpoints included: length of hospitalization, postoperative complications, and pulmonary function, as well as multiple perioperative functional status scores. The feasibility of "Internet Plus" management and patient implementation were assessed.

4. Sample size and statistical methods

The design of this study was a prospective randomized controlled study, and the sample size of this study was based on the difference in the primary outcome 6-minute walk test distance (6MWD) between the two groups at 30 days postoperatively. It is currently recognized that a difference of 30m in a patient's 6MWD is clinically significant. According to the pre-test of the research team, the standard deviation of the 6MWD was 40 m. The probability of class I error was calculated as 0.05 bilaterally and $\beta=0.2$ to obtain 29 patients in each of the two groups, and 32 patients in each of the two groups were taken to account for the

10% shedding of medical records.

The statistical software for this study was in R language (R Foundation for Statistical Computing, Vienna, Austria; version 3.5.2). Measurements were expressed as mean \pm standard deviation or quartiles, depending on the distribution, and counts were expressed as frequencies. In this study, for the primary outcome 6MWD, as well as for the WHODAS 2.0, and the HADS psychological scores, repeated measurements were taken at different time points in the same patient. Considering the correlation between multiple measurements, a linear mixed-effects model was developed in this study to analyze the effect of the intervention. Intervention factors, time points as categorical variables, and interactions between intervention factors and time as fixed effects were included in the model. When there was no evidence in the model suggesting an interaction between the intervention and time, it was removed from the model to estimate the effect of the intervention on the primary outcome at all time points and the effect of time on the primary outcome. Also, given the potential bias of patients missing visits, we will perform sensitivity analyses of the worst measurements for all patients with missing 6MWD data and determine whether missing data have an impact on the analysis of the primary outcome. For other single-measure secondary outcomes, group comparisons were performed using the paired t test for measures that satisfied normality and the nonparametric Mann-Whitney U test for measures that did not satisfy normality. Count data were expressed as frequencies, and intergroup comparisons were performed using the χ^2 test. The test level was $\alpha=0.05$. A statistically significant difference was defined as a two-sided $P<0.05$.

5. Patient inclusion and exclusion criteria

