5.1 Inclusion

- 1) Age: 18-75 years;
- 2) 64 adults with suspected lung cancer proposed for VATS lobectomy/sublobar resection.

5.2 exclusion:

- 1) Patient refusal;
- 2) ASA classification III or higher;
- 3) Pre-neoadjuvant chemotherapy;
- 4) Inability to cooperate (psychiatric abnormalities, impaired consciousness, mental retardation);
- 5) Comorbidities cannot tolerate home rehabilitation or functional motor examination;
- 6) Inability to use a smartphone or read Chinese;
- 7) Average weekly moderate-intensity/high-intensity exercise of >90min/>60min.

6. Research process

- 1) Patients were assessed for enrollment criteria at the time of their initial outpatient visit and decision to proceed with surgery. After obtaining informed consent from the patients, basic information (basic, past medical history, metabolic equivalents, etc.), smoking status, ASA classification, metabolic equivalents, 6MWD, lung function, grip strength, NRS 2002 nutritional risk screening, HADS and WHODAS 2.0 scores were collected
- 2) Both groups were given routine preoperative anesthesia clinic visits and

guidance, and a short-term home multimodal prehabilitation intervention strategy of about 2 weeks, including smoking cessation, aerobic exercise, impedance training, respiratory exercise, nutritional guidance, whey protein powder supplementation and psychological support. Elastic bands, whey protein powder and respiratory trainers were distributed to patients in both groups.

The “Internet+” team trained patients on the online application of the “Preoperative Family Prehabilitation Program” . The patients used the online application for prehabilitation, followed the exercises, and used the sports bracelet as a wearable device to adjust the exercise intensity and record the exercise time.

Patients in the traditional group were issued a portable finger oxygenator to assist in the completion of exercises, as well as a Pre-Rehabilitation Manual and Completion Record Form, which patients were instructed to fill out daily, and patients were followed up twice a week.

Comprehensive reference to previous studies and prior research by the group, combined with patient execution, to propose a concise and easy-to-follow exercise program:

- i) Tobacco and alcohol cessation
- ii) Aerobic exercise

Aerobic exercise is the core of exercise training in a way that consists of two steps, the first step being a 5-minute warm-up process. The second

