[figure not shown]
performed twice a day for 10 minutes each time, and respiratory exercises include balloon blowing, three-ball instrument, respiratory trainer, and active cycle breathing techniques. Individualized protocols are developed based on the patient's underlying respiratory function and tolerance.

v) Dietary and psychological adjustments

The European Society of Clinical Nutrition and Metabolism recommends a daily protein intake of 1.2g/kg-1.5g/kg (ideal weight for obese patients) for surgical patients. Patients are advised to change unhealthy dietary habits, especially high-calorie and high-fat diets, and increase the intake of vegetables, fruits and high-quality proteins (fish, chicken breast and other lean meats, milk, eggs, soybeans) as appropriate. In addition, patients are advised to supplement high-quality protein, such as whey protein powder, one hour before exercise every day to better promote muscle synthesis according to their individual conditions. Encourage patients to perform self-psychological adjustment and listen to relaxing music to sleep before bedtime every day.

The 6MWD at 30 days postoperatively was used as the primary assessment of functional status and the primary endpoint of the study (enrollment, preoperative and 30 d postoperative); secondary endpoints included pulmonary function, length of hospital stay, ICU stay, postoperative complications, and hospitalization costs, and the HADS assessed perioperative psychosocial, the QoR-15 scale assessed

near-term prognosis, and the WHODAS-2.0 scale assessed mid-term prognosis.

7. Research quality control

- 1) All 6-minute walk tests were measured by a unified person, conducted in accordance with international standard procedures and equipped with first-aid

medicines, so that patients could be dealt with in a timely manner if they felt unwell or needed to take a rest;

2) The whey protein powder provided free of charge to the patients was selected from "Nerishi" isolate whey protein powder through the Nutrition Department of the hospital, taking into consideration the purity, purification method, safety, taste and other issues;

3) For patients in the traditional prehabilitation group who have no wearable devices, patients are provided with free finger oxygen meters to facilitate patients to record their heart rate during aerobic exercise, adjust the intensity of exercise, and ensure the safety and effectiveness of exercise;

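### Does the app's 6MWD self-test give the Internet+ arm unequal practice of the primary outcome test?

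*Combined protocol and SAP*

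**What the plan says.** Section 3.1 sets out what the app is to contain. Item 5 is an assessment module with questionnaires and a walking self-test: "patients can complete the self-measurement of 6MWD according to the prompts of the application". Item 6 adds reassessment, adjustment of the programme and daily reminders, but does not tie any of these to the walking test.

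Section 6, item 2 describes what each arm did. For the Internet+ arm: "The patients used the online application for prehabilitation, followed the exercises", with a bracelet to guide and record exercise. Controls received a finger oximeter, "as well as a Pre-Rehabilitation Manual and Completion Record Form, which patients were instructed to fill out daily". No walking self-test is listed there for either arm.

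Section 3.2 dates prehabilitation "from the time the doctor and the patient jointly decided to have the surgery to 1 day before the surgery", and 6MWD is assessed at enrollment, before surgery and 30 days after surgery. Sections 4 and 6 place the primary endpoint at day 30. Section 7, item 1 states: "All 6-minute walk tests were measured by a unified person, conducted in accordance with international standard procedures".

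**The concern.** Distance on a walking test can rise because the patient knows the test better, without any change in function. If one arm can rehearse the test at home and the other cannot, such a gain would be read as a benefit of Internet+ management. A single assessor does not remove it, because it lies in the patient's performance and not in the measurement.

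The preoperative visit is the most exposed, since app-led prehabilitation ends the day before surgery. That visit matters in two ways. Section 3.2 names it in the aim, which concerns the effect of "prehabilitation management on preoperative functional status and prognosis of patients undergoing VATS surgery compared to the traditional model". It also enters the primary mixed model, where Section 4 says of the group-by-time term: "When there was no evidence in the model suggesting an interaction between the intervention and time, it was removed from the model". Once that term is dropped, the effect is estimated over all visits, and part of a preoperative gain reaches the pooled estimate. The documents describe no practice walk for both arms and do not say that the function was switched off for trial patients.

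**Working it through.** **Inputs from Section 4.** Target difference 30 m, SD 40 m, two-sided alpha 0.05, beta 0.2, 29 per arm before dropout.

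**The plan's own figure.** The normal approximation gives 2 × (40 × (1.960 + 0.842) / 30)² = 27.9, so 28 per arm. The t-test version gives 29 (power 80.1%; 28 per arm gives 78.7%). The stated 29 is reproduced.

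**Inputs that are assumed.** The documents give no practice gain, so 5, 10 and 20 m are tried, each applied to every Internet+ patient with no true effect. Within-patient correlation r is taken as 0.5 or 0.8. The threshold for keeping the interaction is taken as 0.05, because Section 4 states none.

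**One visit alone.** SE = 40 × √(2/29) = 10.50 m.
- 5 m: 5/10.50 = 0.48 SE, 17% of the target; false-positive rate 7.6%.
- 10 m: 10/10.50 = 0.95 SE, 33% of the target; false-positive rate 15.9%.

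These rates apply only to a visit that carries the full gain. They apply to day 30 only if the gain lasts until then.

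**Gain at the preoperative visit only, following Section 4's rule.** With the interaction dropped, the estimate over three visits carries one third of the gain: 10/3 = 3.3 m or 20/3 = 6.7 m. The full rule was simulated with 29 per arm, three equally correlated visits and an interaction F test on 2 and 112 df. The pooled test was used if the interaction was dropped, and the day-30 test if it was kept.

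| Assumed preoperative gain | False positive, pooled or day-30 result (r = 0.5 / 0.8) | Interaction kept and preoperative contrast falsely significant (r = 0.5 / 0.8) |
|---|---|---|
| 0 m | 5.6% / 5.2% | 0.9% / 0.5% |
| 5 m | 6.2% / 5.5% | about 2% / 2% |
| 10 m | 7.2% / 6.1% | 5.7% / 7.9% |
| 20 m | 9.0% / 5.7% | 31% / 43% |

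The increase over the no-gain row is 0.6 and 0.3 points at 5 m, and 1.6 and 0.9 points at 10 m. At 20 m with r = 0.8 the interaction is found in 88% of runs, so the gain is mostly kept out of the pooled estimate; with r = 0.5 it is found in 48%. The excess over 5% in the no-gain row comes from the two-stage rule itself and has nothing to do with the self-test. A plain day-30 comparison stays at 5% in every row.

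**The text side by side.** Section 3.1 says what the app allows. Section 6 says what trial patients did, and no self-test is listed. Section 7 says who measured the walk tests. Taken together, the assessor's three walks are the outcome data and the self-test is an optional feature whose use in the trial is not stated.

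**The case for a change.** The strongest case for acting is that each step of the mechanism is supported by the text: the outcome test is in the app, only one arm is described as using the app, the period of use falls between two assessor tests, and nothing equalises familiarity. The remedy looks nearly free, since one function could be locked until the day-30 test, or self-tests could be counted per patient from app records.

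The opportunity for unequal practice does stand. That it occurred, and that it moved the distance walked, does not follow from the documents. Even the claim that controls had no access to the module is an inference from their paper-based management.

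The remedy is also less free than it seems. Section 2, purpose 4 sets out "Evaluation of the clinical feasibility and clinical significance of Internet + wearable device prehabilitation applied to VATS surgery for lung cancer". Self-measurement is part of that package and may feed the reassessment and adjustment in Section 3.1, item 6. Locking it would test a reduced app, and whether that is worth a possible preoperative bias is a matter on which statisticians could reasonably differ. A count of self-tests would describe an imbalance without removing it or altering any estimate.

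**Conclusion.** No change to the plan is called for. Unequal practice is possible but not shown, and the primary endpoint is well placed against it: day 30 comes after app-led prehabilitation has ended, and by then both arms have taken two assessor walks. For an assumed 5 to 10 m gain confined to the preoperative visit, the pooled or day-30 false-positive rate rises by roughly 0.3 to 1.6 points. The 31% and 43% figures for the preoperative contrast need 20 m, two thirds of the target difference, in every Internet+ patient.

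These figures rest on the assumed gains, correlations and interaction threshold, and on the gain not lasting to day 30. If a whole-arm gain did last, the single-visit rates of about 8% (5 m) and 16% (10 m) would apply there; nothing in the documents indicates that it would. Whether trial patients used the self-test is a gap in description. Analysts will fill it sensibly by taking the assessor-measured walks as the outcome and reading the preoperative contrast with the app's content in mind.

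### The mixed model for 6MWD, WHODAS 2.0 and HADS makes inefficient use of the enrollment value, and dropping the interaction would average enrollment into the group effect

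*Combined protocol and SAP*

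**What the plan says.** Section 4 puts 6MWD, WHODAS 2.0 and HADS into a linear mixed model and lists its fixed effects: "Intervention factors, time points as categorical variables, and interactions between intervention factors and time as fixed effects were included in the model". If there is no evidence of an interaction, "it was removed from the model to estimate the effect of the intervention on the primary outcome at all time points".

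For 6MWD, Section 3.2, item 3, states that "patients were evaluated at enrollment, before surgery, and 30 days after surgery". The endpoint paragraph of Section 6 repeats the three visits: "the primary endpoint of the study (enrollment, preoperative and 30 d postoperative". Section 6, item 1, confirms that the enrollment values exist for all three outcomes: "6MWD, lung function, grip strength, NRS 2002 nutritional risk screening, HADS and WHODAS 2.0 scores were collected".

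The sample size in Section 4 is "based on the difference in the primary outcome 6-minute walk test distance (6MWD) between the two groups at 30 days postoperatively", and Section 6 also gives day-30 6MWD as the primary endpoint. Nowhere does the plan mention an enrollment covariate, a common enrollment mean, a covariance structure, or which model contrast is the primary one.

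**The concern.** Enrollment is one of the listed 6MWD visits, time is categorical, and enrollment is not a covariate. The natural reading is therefore that enrollment is an outcome row with its own free group difference. Two things follow.

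- **Efficiency.** With complete data, the model's day-30 contrast is the raw day-30 difference, which gains nothing from enrollment. Its interaction contrast against enrollment is an unadjusted change score, which uses enrollment inefficiently. Modelling the within-patient correlation does not adjust for baseline while the enrollment means are free to differ by group. Because the plan does not say which contrast is primary, the choice between them is also left open.
- **Dilution.** Enrollment precedes the intervention, so randomization makes its expected group difference zero. Once the interaction is removed, the single group effect averages that zero in with the two later visits. The result is no longer the day-30 difference on which the trial was sized, and it will usually be smaller.

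**Working it through.** **Inputs from Section 4.** Two-sided alpha 0.05, power 80%, difference 30 m, SD 40 m, 29 evaluable per arm (32 with dropout). **Assumed.** The correlation rho between enrollment and day-30 6MWD is not given; 0.3, 0.5, 0.6 and 0.7 are used.

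**1. The plan's own figure.** The normal approximation, 2 × [40 × (1.96 + 0.84)/30]², gives 27.9, so 28 per arm. The noncentral t gives 78.7% power at 28 and 80.1% at 29. The stated 29 reproduces, and 29 × 1.1 = 31.9 gives the stated 32.

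**2. Efficiency at 29 per arm.** The effective SD is 40 for the raw day-30 difference (56 df), 40√[2(1−rho)] for the change score (56 df) and 40√(1−rho²) with adjustment (55 df). The SE is the effective SD × √(2/29).

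| rho | 0.3 | 0.5 | 0.6 | 0.7 |
|---|---|---|---|---|
| SE raw, m | 10.5 | 10.5 | 10.5 | 10.5 |
| SE change, m | 12.4 | 10.5 | 9.4 | 8.1 |
| SE adjusted, m | 10.0 | 9.1 | 8.4 | 7.5 |
| Power raw, % | 80.1 | 80.1 | 80.1 | 80.1 |
| Power change, % | 66.0 | 80.1 | 88.1 | 95.2 |
| Power adjusted, % | 83.7 | 90.0 | 93.9 | 97.5 |
| Gain over the better unadjusted contrast, points (unrounded powers) | 3.5 | 9.8 | 5.9 | 2.4 |
| Detectable with 80% power, adjusted, m | 28.6 | 25.9 | 24.0 | 21.4 |
| Detectable with 80% power, change, m | 35.4 | 29.9 | 26.8 | 23.2 |

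The raw contrast detects 29.9 m throughout. A simulation of 20,000 trials per rho, with the covariate slope estimated, gave adjusted power of 83.4/89.5/93.3/97.2%.

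**3. Chance imbalance.** One SE at enrollment is 40 × √(2/29) = 10.5 m. It shifts the raw contrast by rho × 10.5 = 3.2/5.3/6.3/7.4 m. It shifts the change score by (1−rho) × 10.5 = 7.4/5.3/4.2/3.2 m in the opposite direction.

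**4. Removing the interaction.** With equal correlations between visits, the single group effect is the simple mean over the three visits. True effects of 0/30/30 m give (0 + 30 + 30)/3 = 20 m. The SE is 40 × √[(1 + 2rho)/3 × 2/29], which is 8.6 m at rho 0.5. The power of the pooled test is then about 63% (noncentral t, 56 df), against 80.1% for the plain day-30 comparison.

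**5. How often the rule acts.** This takes absence of evidence to mean p ≥ 0.05 on the 2-df interaction test (F with 2 and 112 df). The noncentrality is (29/2) × Σ(d − mean d)²/[1600(1−rho)]. For 0/30/30 m, Σ = 400 + 100 + 100 = 600; at rho 0.5 the noncentrality is 14.5 × 600/800 = 10.9.

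| rho | 0.3 | 0.5 | 0.6 | 0.7 |
|---|---|---|---|---|
| Interaction removed, true 0/30/30 m, % | 31 | 16 | 9 | 3 |
| Interaction removed, true 0/20/20 m, % | 64 | 52 | 43 | 29 |

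Simulation for 0/30/30 m gave 30.4/16.4/8.5/2.8%. With equal correlations and complete data, the visit mean is independent of the interaction test, so the average of 20 m also holds within the trials where the rule acts.

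**The case against.** A model with group, time and their interaction is a recognised analysis. The raw day-30 contrast is unbiased, and the trial has its planned power without adjustment. The efficiency gain depends on a correlation that the documents do not give. It fades outside the middle of the range: over the better unadjusted contrast it is 2.4 points at rho 0.7 and 0.3 at 0.8. The imbalance shift is also not a separate benefit, because that variation is already in the SE. All of this stands, which is why the efficiency half is presented as a gain from existing data and not as the correction of an error.

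On dilution, the plan never says outright that enrollment is an outcome row, and the 20 m figure is conditional on removal. Averaged over all trials, the loss for 0/30/30 m is at most about 3.1/1.6/0.9/0.3 m (10 m × the removal rate). For 0/20/20 m it is at most about 4.3/3.5/2.8/1.9 m (20 − 13.3 = 6.7 m × the removal rate). A pre-surgery effect well above the day-30 effect would offset it: 0/45/30 m pools to 25 m, and 0/60/30 m to 30 m. The equal weights assume equal correlations. The removal sentence names only the primary outcome, and no later visits or SDs are given for WHODAS 2.0 or HADS.

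These points limit the size; they do not remove the problem. If enrollment is not an outcome row, the dilution vanishes, but the enrollment value is then unused and the case for adjustment is stronger. Under first-order autoregressive correlation, with 0.5 to 0.8 between adjacent visits, the enrollment weight rises from one third to 0.40–0.45. The rule also acts most often when the effect is modest.

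**Conclusion.** The concern holds, and the plan should be changed. Adjustment for enrollment is worth at most about 10 points of power over the better unadjusted contrast, near rho 0.5, and less elsewhere. It also removes the shift from chance enrollment imbalance. The removal rule is the more serious half: when it acts, a true 0/30/30 m effect is reported as about 20 m, below the 30 m that Section 4 treats as clinically significant. That happens in about 31% of trials at rho 0.3 and 3% at rho 0.7, and in 64% to 29% for a true 0/20/20 m effect.

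These figures assume complete data on 29 per arm, SD 40 m at every visit, an assumed rho and, for the removal rule, enrollment as an outcome row with equal correlations. They apply to 6MWD only. Neither half by itself inflates the type I error of a single prespecified contrast, and the sample size is adequate on its own assumptions.

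**What to change.** - **Model.** Use a constrained longitudinal model: enrollment, pre-surgery and day-30 values as outcomes, one common enrollment mean for both groups, and an unstructured covariance. Alternatively, model the pre-surgery and day-30 values with the enrollment value and its interaction with time as covariates.
- **Primary contrast.** Name the day-30 group difference in 6MWD as the primary contrast.
- **Removal rule.** Delete it. Keep the group-by-time terms whatever their p-value, so that enrollment is never pooled into one group effect.
- **Other outcomes.** Use the same model for WHODAS 2.0 and HADS. If lung function is measured again after enrollment, which the plan does not state, adjust that comparison for its enrollment value too.

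The cost is statistical wording only, with no new data, visits or patients. The constrained model has one fixed-effect parameter fewer than the planned one (5 against 6). Its unstructured covariance has 6 parameters at three visits, against 2 for a random intercept, which is one possible reading of the plan. The covariate version adds the enrollment value and its interaction with time.
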